Appendix 2 lists the laboratory tests that will be performed for this study.

Appendix 4 lists the hepatic monitoring tests for treatment-emergent abnormality.

All study assessments except for the C-SSRS, Self-Harm, and Self-Harm Follow-Up will be completed electronically.

For all assessments, the same assessor should perform each assessment for a given patient during the study to minimize interobserver variation.

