6.1. General Considerations

This plan describes a priori statistical analyses that will be performed. Statistical analysis of this study will be the responsibility of Eli Lilly and Company (hereafter Lilly). The statistical analyses will be performed using SAS® Version 9.2 or higher. Lilly will be responsible for producing the tables, figures, and listings, unless otherwise specified. All tables, figures, and listings will be checked independently for consistency and integrity by Lilly. This analysis plan also includes exploratory analyses that are intended to be produced separately from the clinical study report (CSR) outputs, as noted below.

Additional efficacy, health outcomes, and safety analyses for Health Technology Assessment (HTA) purposes will be described in a separate document, and results will be reported separately from the CSR.

Continuous data will be summarized in terms of the number of observations, mean, standard deviation (SD) and/or standard error of the mean (SEM), if applicable, median, minimum, and maximum. The minimum and maximum will be reported to the same number of decimal places as the raw data recorded in the database. The mean and median will be reported to 1 more decimal place than the raw data recorded in the database. The SD and SEM will be reported to 2 more decimal places than the raw data. In general, the maximum number of decimal places reported shall be 4 for any summary statistic.

Categorical data will be summarized in terms of the number of patients in the analysis population, the number of patients with non-missing data at the relevant time point, frequency counts, and the percentages based on the appropriate method. Percentages will be presented to 1 decimal place. Percentages will not be presented for zero counts.

Change from baseline will be calculated as the post-baseline value minus the baseline value. Percent change from baseline is defined as $(100 \times [\text{post-baseline} - \text{baseline}] / \text{baseline})$. Percent improvement from baseline is calculated as the positive percent change from baseline if a higher value at post-baseline means improvement from baseline. Similarly, percent improvement from baseline is calculated as the negative percent change from baseline if a lower value at post-baseline means improvement from baseline. If the baseline value is missing for a particular variable, then the change from baseline and the percent improvement from baseline will not be calculated.

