6.4. Handling of Dropouts or Missing Data

6.4.1. Non-Responder Imputation (NRI) for Clinical Response

Analysis of categorical efficacy and health outcome variables will be based on treatment success/failure. This approach yields results numerically identical to non-responder imputation (NRI), but it is interpreted differently. Patients will be considered treatment failures (or non-responders) if they do not meet the clinical response criteria or have missing clinical response data at a particular time point of analysis.

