Psoriasis Area and Severity Index (PASI)	
For patients with plaque psoriasis, combines assessments of the extent of body-surface involvement in 4 anatomical regions (head and neck, trunk, arms, and legs) and the severity of scaling (S), redness (R), and plaque induration/infiltration thickness (T) in each region, yielding an overall score of 0 for no psoriasis to 72 for the most severe disease (Fredriksson and Pettersson 1978). Severity is rated for each index (R, S, T) on a 0-4 scale (0 for no involvement; up to 4 for very severe involvement):
 
0 = none 1 = slight 2 = moderate 3 = severe 4 = very severe
 
The body is divided into 4 anatomical regions comprising the head (h), upper limb (u), trunk (t), and lower limb (l). In each of these areas, the fraction of total BSA affected is graded on a 0-6 scale (0 for no involvement; up to 6 for 90% to 100% involvement): 0 = 0% (clear)
	PASI total score Total PASI score ≤ 1 , ≤ 2 , or ≤ 3	
The composite PASI score is calculated by multiplying the sum of the individual-severity scores for each area by the weighted area-of-involvement score for that respective area, and then summing the 4 resulting quantities as follows:
 $\text{PASI} = 0.1(R_h + T_h + S_h)A_h + 0.2(R_u + T_u + S_u)A_u + 0.3(R_t + T_t + S_t)A_t + 0.4(R_l + T_l + S_l)A_l$ 
Where, R_h, R_u, R_t, R_l = redness score of plaques on the head, upper limb, trunk, and lower limb, scored 0-4 respectively; T_h, T_u, T_t, T_l = thickness score of plaques on the head, upper limb, trunk, and lower limb, scored 0-4 respectively; S_h, S_u, S_t, S_l = scaliness score of plaques on the head, upper limb, trunk, and lower limb, scored 0-4 respectively; A_h, A_u, A_t, A_l = numerical value translation of % area of psoriatic involvement score for the head,
	If any individual score is missing, the PASI score will not be calculated, hence missing.

Measure	Description	Variable	Derivation/Comment	Imputation Approach if with Missing Components
	1 = >0% to <10% 2 = 10% to <30% 3 = 30% to <50% 4 = 50% to <70% 5 = 70% to <90% 6 = 90% to 100% The various body regions are weighted to reflect their respective proportion of BSA.		upper limb, trunk, and lower limb, respectively. PASI scores are treated as a continuous score, with 0.1 increments within these values.	
		
 Change from baseline in PASI total score 	Calculated as: observed PASI score – baseline PASI score	Missing is baseline or observed value is missing

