		
 PASI 75/90/100 	Defined as at least 75%, 90%, or 100% improvement in PASI total score from baseline	Single item, missing if PASI total score is missing
ACR50 and PASI 100	Patients who achieve ACR50 and PASI 100 simultaneously.	
 Simultaneous ACR50 and PASI 100 		Missing if either ACR score or PASI score is missing.
Percentage of Body Surface Area (BSA)	The investigator will evaluate the percentage involvement of psoriasis on each patient’s BSA on a continuous scale from 0% (no involvement) to 100% (full involvement), in which 1% corresponds to the size of the patient’s hand (including the palm, fingers, and thumb) (National Psoriasis Foundation [NPF] 2009).	
 BSA 	Collected as a single item on the eCRF. Range from 0% to 100%	Single item, missing if missing.
		
 Change from baseline in BSA 	Calculated as: observed BSA – baseline BSA	Missing is baseline or observed value is missing

Measure	Description	Variable	Derivation/Comment	Imputation Approach if with Missing Components

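### The PASI missing-item rule has no exception for clear regions, so a blank that cannot change the score can turn a known responder into a non-responder

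*SAP*

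**What the plan says.** SAP Section 6.12, Table RHCF.6.3, derives PASI by "multiplying the sum of the individual-severity scores for each area by the weighted area-of-involvement score" and adding the four regional results with weights 0.1, 0.2, 0.3 and 0.4. Area is graded 0 to 6, with 0 meaning a clear region. Redness, thickness and scaling are each graded 0 to 4 ("0 for no involvement; up to 4 for very severe involvement").

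The missing-component column for the total reads: "If any individual score is missing, the PASI score will not be calculated, hence missing". It makes no exception for a region with area score 0.

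The consequence is carried forward explicitly:
- PASI 75/90/100: "Single item, missing if PASI total score is missing".
- Composite of ACR50 and PASI 100: "Missing if either ACR score or PASI score is missing".
- SAP Section 6.4.1 counts patients as treatment failures if they "have missing clinical response data at a particular time point of analysis".
- SAP Section 6.1 deals with baseline: "If the baseline value is missing for a particular variable", percent improvement is not calculated.

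**The concern.** Non-responder imputation is meant for outcomes that are unknown. Here the outcome can be known. When the area score is 0, the blank severity item is multiplied by zero, so the total does not depend on it.

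The patients exposed are those with clear regions, and a PASI 100 responder is clear in all four. PASI 100 is half of the primary endpoint and is also the second major secondary endpoint. A misclassification therefore reaches two of the three tests in the SAP Section 6.6 sequence.

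There is also a baseline route. Protocol Section 6.1 requires only 3% body surface area, so a region without psoriasis at Week 0 is plausible. One blank severity item there removes the baseline PASI, and with it percent improvement at every later visit, unless another pre-dose PASI exists to serve as baseline under SAP Section 6.1.1.

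**Working it through.** **1. The algebra.** PASI is the sum over regions of weight × (R + T + S) × A. With A = 0 the term is weight × (R + T + S) × 0 = 0. Evaluating the formula with all four areas at 0 gave 0 for all 125 severity combinations in the head region, and for each common severity value from 0 to 4 entered in every region. The rule discards a score that the formula determines.

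**2. The plan's own figure.** Inputs from SAP Section 5.2: composite rates of 13.6% (adalimumab) and 31.3% (ixekizumab), 275 per arm, two-sided 0.05, stated power approximately 99%.

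Normal approximation, with mean rate 0.2245:
- Difference term: 0.177 × √275 = 2.935.
- Critical term: 1.96 × √(2 × 0.2245 × 0.7755) = 1.157.
- Standard deviation term: √(0.136 × 0.864 + 0.313 × 0.687) = 0.5767.
- z = (2.935 − 1.157)/0.5767 = 3.08, so power is 0.9990.

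Exact Fisher power is 0.9987. The stated figure is reproduced.

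**3. Effect on the composite.** The documents give no blank rate. Let f be the share of true responders in each arm who have such a blank, with f assumed between 0 and 20%. Each rate becomes p × (1 − f), and responders lost are 275 × p × f.

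| f | Adalimumab | Ixekizumab | Responders lost (adalimumab, ixekizumab) | Difference (points) | Relative risk | Odds ratio | Fisher power |
|---|---|---|---|---|---|---|---|
| 0 | 13.6% | 31.3% | 0, 0 | 17.7 | 2.30 | 2.89 | 0.9987 |
| 5% | 12.9% | 29.7% | 1.9, 4.3 | 16.8 | 2.30 | 2.85 | 0.9978 |
| 10% | 12.2% | 28.2% | 3.7, 8.6 | 15.9 | 2.30 | 2.81 | 0.9963 |
| 20% | 10.9% | 25.0% | 7.5, 17.2 | 14.2 | 2.30 | 2.74 | 0.9905 |

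The odds ratios are unadjusted. At f = 0: (0.313/0.687)/(0.136/0.864) = 2.89. At f = 20%: (0.2504/0.7496)/(0.1088/0.8912) = 2.74. The factor (1 − f) cancels from the relative risk.

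**4. Effect on PASI 100** (23.7% vs 46.9%). The difference goes from 23.2 points to 22.0, 20.9 and 18.6 at f = 5%, 10% and 20%. The odds ratio goes from 2.84 to 2.77, 2.69 and 2.57. Power at f = 20% is 0.9978.

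**5. Type I error.** If the true rates are equal and f is the same in both arms, the observed rates are also equal. The null hypothesis is preserved.

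**6. Stress case.** If only ixekizumab responders were affected, the composite difference would be 14.6 points with 98.6% power at f = 10%, and 11.4 points with 91.4% power at f = 20%. Nothing in the documents suggests this: PASI is scored by a blinded assessor (Protocol Section 7.3), and Week 0 PASI belongs to the baseline assessment.

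**The case against.** The strongest reply is that the problem may never arise. The severity scale provides a 0 for clear skin, so a blank is an omission and not the natural entry. Protocol Section 9 states: "All study assessments except for the C-SSRS, Self-Harm, and Self-Harm Follow-Up will be completed electronically". Protocol Appendix 3.2 provides for programmed edit checks and a database quality review. SAP Table RHCF.6.9 lists missing ACR or PASI data at any visit as an important violation. All of this stands, and the case data-capture form is not in the documents. It makes blanks less likely but does not exclude them. Flagging a blank also does not restore the patient's response.

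A strict rule is not unique to PASI: LEI, SPARCC and DAS28-CRP are also set to missing when a component is missing. In those scores, however, a missing component generally leaves the total undetermined. Where the available items settle the result, the SAP uses them: ACR response (Appendix 2), PsARC and MDA all work this way. The ACR half of the composite therefore follows a principle that the PASI half does not.

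A reader might infer that clear patients will routinely be lost, or that the primary result is in jeopardy. The documents support neither. No blank rate is given, and the values of f are assumptions, not estimates of harm. The primary analysis is a logistic regression reporting odds ratios, and on that scale the movement is small. The ACR50 noninferiority test does not use PASI at all. Nor does the rule favour ixekizumab: with equal f, the arm with more clear skin loses more responders, so the absolute difference shrinks.

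**Conclusion.** The point holds as a defect in a stated rule, with a conditional and probably small effect. Whenever a severity item is blank in a region scored as clear, the rule replaces a determined PASI with a missing value, and a known responder can be counted as a failure. How often this happens cannot be judged from the documents; if the form forces or fills in a 0, it never does.

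Under equal blank rates in both arms, the cost is understated response rates and an understated absolute difference, by 0.9 to 3.5 composite points over the assumed range (17.7 − 16.8 and 17.7 − 14.2). The relative risk is unaffected, and the planned conclusions are not threatened. The power figures use Fisher's test, as in the plan's sample-size section, and not the logistic model. The correction is worth making because it only evaluates the SAP's own formula, and it leaves results unchanged if no such blanks exist.

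**What to change.** In SAP Table RHCF.6.3, replace the PASI missing-component rule with: *If a region's area score is 0, that region contributes 0 regardless of its severity scores; otherwise, if any individual score is missing, PASI is missing.* A blank area score would still make PASI missing.

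Apply the rule at baseline and after baseline, to total PASI, PASI 75/90/100, the absolute PASI thresholds and the composite. Leave the Table RHCF.6.9 check for missing ACR or PASI data on the raw items, so that incomplete assessments are still flagged; moving that check to the new derivation would weaken a data-completeness control.

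The cost is one SAP sentence and one line of derivation code, with no change to data collection. It should be settled before the Week 24 database lock, to avoid a post hoc decision on the primary endpoint. Confirming how the form handles severity fields when area is 0 would show whether the change has any practical effect.

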Nail Psoriasis Severity Index (NAPSI)	NAPSI will be used if the patient has fingernail psoriasis at baseline. The NAPSI is a numeric, reproducible, objective tool for evaluation of fingernail psoriasis. This scale is used to evaluate the severity of fingernail bed psoriasis and fingernail matrix psoriasis by area of involvement in the fingernail unit. In this study, only fingernail involvement will be assessed. The fingernail is divided with imaginary horizontal and longitudinal lines into quadrants. Each fingernail is given a score for fingernail bed psoriasis (0-4) and fingernail matrix psoriasis (0-4), depending on the presence (score of 1) or absence (score of 0) of any of the features of fingernail bed and fingernail matrix psoriasis in each quadrant: 0 = None 1 = present in one quadrant of nail 2 = present in two quadrants of nail 3 = present in three quadrants of nail 4 = present in four quadrants of nail	
 NAPSI score 	The NAPSI score of a fingernail is the sum of scores in fingernail bed and fingernail matrix from each quadrant (maximum of 8). Each fingernail is evaluated, and the sum of all the fingernails is the total NAPSI score (range, 0 to 80), usually indicated as NAPSI score.	For each fingernail, if either the bed or matrix score is missing or not done, then the score for that finger is missing. If <50% of the finger scores from 10 fingers are missing, the imputation will be performed by using the average score of the remaining fingernails. If ≥50% of the finger scores are missing, the NAPSI score will be left as missing
		
 Change from baseline in NAPSI score 	Calculated as: observed NAPSI – baseline NAPSI	Missing if baseline or observed value is missing
		
 NAPSI = 0 	NAPSI score equals to 0, indicating resolution of nail psoriasis.	Single item, missing if observed NAPSI score missing.
Tender Joint Count (TJC) (68 joint count)	The number of tender and painful joints will be determined by examination of 68 joints (34 joints on each side of the patient’s body). The 68 joints to be assessed and classified	
 TJC score 	Adjusted sum of the painful/tender joints for all 68 joints: (sum of the evaluable individual joint	If more than half of the joint scores are nonevaluable, the total score will be missing.

Measure	Description	Variable	Derivation/Comment	Imputation Approach if with Missing Components

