	
a patients' disease (Coates et al. 2010a; Coates and Helliwell 2010b). The LEI is used to assess tender enthesal points.
		
measures: TJC ≤ 1 SJC ≤ 1 PASI total score ≤ 1 or BSA ≤ 3 patient pain VAS score of ≤ 15 patient global assessment VAS score of ≤ 20 HAQ-DI score ≤ 0.5 tender enthesal points (6 enthesal points) ≤ 1
	
the result is missing.

Coates criteria for Minimal Disease Activity (MDA) (18 enthesal points)
	
Uses a composite of 7 key outcome measures (includes PASI) used in PsA to encompass all of the domains of the disease to measure the overall state of a patients' disease (Coates et al. 2010a; Coates and Helliwell 2010b). The LEI and SPARCC are used to assess tender enthesal points.
	
Proportion of patients achieving Coates criteria for MDA (18 enthesal points)
	
Patients are classified as achieving Coates criteria for MDA (18 enthesal points) if they fulfill 5 of 7 outcome measures: TJC ≤ 1 SJC ≤ 1 PASI total score ≤ 1 or BSA ≤ 3 patient pain VAS score of ≤ 15 patient global VAS score of ≤ 20 HAQ-DI score ≤ 0.5 tender enthesal points ≤ 1 (based on 18 enthesal points)
	
If the patient achieves MDA with the non-missing measures, then impute as achieving MDA; otherwise, the result is missing.

Leeds Enthesitis Index (LEI)
	
For patients with enthesitis, an assessment that consists of 18 enthesal points is performed by site personnel. The LEI has been developed specifically for use in PsA and measures enthesitis at 6 sites (lateral epicondyle [left and right],
	
LEI score
	
Each of the 6 sites is assigned a score of 0 (absent) or 1 (present) and the results are added to produce a total score (range: 0-6).
	
If one or more of the 6 sites are missing, then set LEI score to missing.

		
Change from baseline in LEI
	
Calculated as: observed LEI score – baseline LEI score
	
Missing if baseline or observed value is missing

Measure	Description	Variable	Derivation/Comment	Imputation Approach if with Missing Components
	medial femoral condyle [left and right], and Achilles tendon insertion [left and right]) (Healy and Helliwell 2008).	
 LEI score = 0 	LEI score equals to 0, indicating complete resolution in enthesitis.	Missing if observed value are missing

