		ANCOVA model using mBOCF (see Section 6.4.2)	ITT population - patients with baseline fingernail involvement (NAPSI >0)	IXE vs ADA at or after Week 12	Secondary analysis
	Proportion of patients with complete resolution in nail psoriasis (NAPSI = 0)	Logistic regression using the NRI method (see Section 6.4.1)	ITT population - patients with baseline fingernail involvement (NAPSI >0)	IXE vs ADA at each post-baseline visit at or after Week 12	Exploratory analysis
		Fisher’s exact test using the NRI method (see Section 6.4.1)	ITT population - patients with baseline fingernail involvement (NAPSI >0)	IXE vs ADA at each post-baseline visit at or after Week 12	Exploratory analysis

Abbreviations: ADA = adalimumab; ANCOVA = analysis of covariance; ITT = intent to treat; IXE = ixekizumab; mBOCF = modified baseline observation carried forward; MMRM = mixed-effects model of repeated measures; NRI = non-responder imputation.

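### The exploratory NAPSI = 0 analysis can credit complete nail resolution when the affected nail was never scored, because unscored nails are filled from the average of clear ones

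*SAP*

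**What the plan says.** All of this is in SAP Section 6.12.

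**Table RHCF.6.3, NAPSI score.** Each nail has a bed score (0 to 4) and a matrix score (0 to 4), and "the sum of all the fingernails is the total NAPSI score (range, 0 to 80". For a single nail, "if either the bed or matrix score is missing or not done, then the score for that finger is missing". For the total, "If <50% of the finger scores from 10 fingers are missing", then "the imputation will be performed by using the average score of the remaining fingernails". Otherwise: "If ≥50% of the finger scores are missing, the NAPSI score will be left as missing".

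**Table RHCF.6.3, NAPSI = 0.** The variable is defined as "NAPSI score equals to 0, indicating resolution of nail psoriasis". It is treated as a single item that is missing only when the visit's NAPSI score is missing. Nothing requires all nails, or the nails affected at baseline, to have been scored.

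**Table RHCF.6.4.** The analysis variable is "Proportion of patients with complete resolution in nail psoriasis (NAPSI = 0"). It is compared between arms from Week 12 on by logistic regression and Fisher's exact test with nonresponder imputation (NRI), in patients with baseline NAPSI above 0, and is labelled exploratory.

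**Other scores in Table RHCF.6.3.** For LEI the rule is "If one or more of the 6 sites are missing, then set LEI score to missing". SPARCC and LDI-B are also set to missing when any site is missing, and PASI is not calculated if any individual score is missing.

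**The concern.** A claim of complete resolution says that no disease is left. Here it can rest on nails nobody scored. When all scored nails are clear, their average is 0, so the rule assumes that the unscored nails are clear too, and the total becomes 0 by construction. If the unscored nail is the one that carried the disease at baseline, the patient is recorded as resolved with no observation of the affected site.

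The rule on partly scored nails makes this sharper. A nail with disease recorded in the bed but no matrix score is treated as wholly missing, so recorded disease can be replaced by an imputed 0.

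NRI, which the SAP relies on for binary outcomes, is no safeguard. Under Section 6.4.1 it acts when the response criterion is not met or the response is missing. A total completed by averaging is neither.

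**Working it through.** **Inputs, from Table RHCF.6.3.** Ten nails; nail score = bed + matrix, at most 8; a nail is unscored if either part is absent. Let k be the number of unscored nails and S the sum over the 10 − k scored nails.

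**Rule as written.**
- If k/10 ≥ 0.5, the total is missing.
- Otherwise total = S + k × S/(10 − k).

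**Check against the stated range.** All ten nails at 8 give 80; all at 0 give 0. This matches the SAP's 0 to 80.

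**Cases at a post-baseline visit.**

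| Situation | Total | NAPSI = 0? |
|---|---|---|
| k = 1, other nine at 0 | 0 + 1 × 0 = 0 | Yes (true total 1 to 8 if that nail is diseased) |
| k = 2, other eight at 0 | 0 | Yes (2 to 16 if both are diseased) |
| k = 3, other seven at 0 | 0 | Yes (3 to 24 if all three are diseased) |
| k = 4, other six at 0 | 0 | Yes (4 to 32 if all four are diseased) |
| k = 5 or more | missing | No, by NRI |
| One nail with bed 4 and matrix not done, other nine at 0 | 0 | Yes, although disease was recorded |
| k = 1, one scored nail at 1, other eight at 0 | 1 + 1/9 = 1.11 | No |

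**Example.** Baseline NAPSI is 8, all on one nail. At Week 24 that nail is not done and the other nine score 0. The total is 0 and the patient is a responder.

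**Direction of the error when k is 1 to 4.**
- If any scored nail is above 0, then S > 0, the total is above 0 and the patient is correctly a nonresponder.
- If all ten nails are truly clear, the total is 0 and the patient is correctly a responder.
- The only misclassification arises when every scored nail is 0 and an unscored nail is diseased. That is a false resolution.

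Averaging cannot produce a false nonresponse, whatever the reason nails are unscored.

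**Conditional illustration.** Suppose d diseased nails remain and m of the ten nails are unscored at random. A false zero needs all d to fall among the m, with probability C(m,d)/C(10,d).
- d = 1: m/10 = 10%, 20%, 30%, 40% for m = 1, 2, 3, 4.
- d = 2: 0/45, 1/45, 3/45, 6/45 = 0%, 2.2%, 6.7%, 13.3%.

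These apply only to a patient who already has diseased nails left and m nails unscored. Turning them into an effect on response proportions would need the frequency of such visits, which neither document gives.

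**The case against.** **The endpoint is peripheral.** NAPSI = 0 is exploratory and outside the testing sequence in SAP Section 6.6; the listed objectives include only change from baseline in NAPSI. This stands and sets the weight of the point.

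**Averaging over observed components is an accepted convention in this SAP.** Joint counts are prorated when at least half the joints are evaluable (Appendix 3), and HAQ-DI is averaged over six to eight answered categories (Appendix 4). So NAPSI is not an outlier as a score. That defends the continuous total. It does less for a variable whose whole content is that no disease remains, and the comparable zero-score outcomes (LEI, SPARCC, LDI-B) and PASI 100 cannot be reached with a component missing.

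**A reader might infer that the SAP contradicts its own treatment-failure principle.** It does not. Section 6.4.1 concerns missing response data at a time point; partly missing components have their own column in Table RHCF.6.3. The two rules are layered, and the gap lies between them.

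**A reader might also infer that mean change in NAPSI is overstated.** The documents do not establish this. If the unscored nail had truly cleared, the imputed change is right. Where a clear nail is unscored among diseased ones, averaging fills it with a positive value and understates improvement. The continuous score can err either way.

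**Unscored nails may be rare.** Protocol Section 9.1.2.12 asks sites to ensure that nails are available for assessment. That is fair, and nothing in the documents shows that diseased nails are the ones more likely to go unscored.

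**The missing-data rule for NAPSI = 0 could mean the score before imputation.** This is possible, but the same table uses the word observed for the visit value as opposed to baseline, and only the case with half or more nails missing stays missing. If the stricter meaning was intended, the SAP should say so.

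**Conclusion.** The point holds for the NAPSI = 0 responder variable and no further. As written, Table RHCF.6.3 credits complete resolution to a patient with one to four unscored nails whenever the scored nails are all 0, even if the affected nail is among the unscored or has bed disease on record. The resulting error has one direction, toward false resolution, and NRI does not remove it.

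This rests on two conditions: the patient had baseline NAPSI above 0, so is in the analysis, and every scored nail at the visit is 0.

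The overall effect cannot be computed and is probably small. The 10% to 40% figures might be taken for an effect size; they are conditional on one remaining diseased nail and on random missingness. Nor do the documents support a between-arm bias: the rule is the same in both arms and a blinded assessor scores the nails. The primary and both major secondary endpoints do not use NAPSI. This is a cheap improvement to an exploratory analysis, not a threat to the trial's conclusions.

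**What to change.** In Table RHCF.6.3, leave the averaging rule in place for the NAPSI score and its change from baseline, and add a condition to the NAPSI = 0 row:

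- NAPSI = 0 is met only if every nail that scored above 0 at baseline, or was unscored at baseline, is actually scored 0 at the visit, and no bed or matrix score recorded at that visit is above 0.
- If any recorded bed or matrix score is above 0, the patient is a nonresponder.
- If neither applies, NAPSI = 0 is missing and handled by NRI.

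The existing rule that the total is missing when half or more of the nails are unscored stays as it is.

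Under this wording the worked example becomes missing and so a nonresponder by NRI, and the patient with bed 4 and no matrix score becomes a nonresponder outright. A patient whose affected nails were all scored 0, and whose only unscored nail was clear at baseline, remains a responder. Requiring all ten nails to be scored 0 would be simpler and closer to the LEI rule, but would cost more nonresponders.

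The cost is a few lines in the SAP and a derivation from the nail-level scores that the NAPSI total already needs. A few patients with an unscored affected nail become nonresponders, some of whom may truly have cleared.
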